### **Conversions**

- 1 year=365.25 days
- 1 month=30.4573 days

## **4.2 Efficacy analysis**

Results of all statistical analyses will be presented using a two-sided 95% confidence interval (CI) and one-sided nominal p-value, unless otherwise stated. In addition, for all primary and key secondary endpoints the asymmetric confidence intervals will be produced as per Frewer P. et. al., 2016, unless otherwise stated. Finally, details of all participants affected by intercurrent events will be summarized in the key participant information output and

participants with missing data for primary and key secondary endpoints will be listed specifying reasons for missingness. Also, the statistical testing process with alpha adjustments at each stage as well as final alpha assignments will be tabulated.

Table 8 below details which efficacy endpoints are to be subjected to formal statistical analysis, making it clear which analysis is regarded as primary for that endpoint.

**Table 8 Pre-planned statistical analyses to be conducted**

Endpoints analysed	Notes

Primary endpoint:  Change in weekly average of daily NRS pain scores from baseline to Week 12
	
MCP-MOD for:
 
 
• Primary analysis 
 
○ Presence of dose response effect for each of the 6 prespecified candidate dose model.
 
 
 
• Supportive analysis 
 
○ Estimation of the dose-response parameters and target dose of MEDI17352 from the chosen model
 
 
 
 
ANCOVA for:
 
 
• Secondary analysis 
 
○ Pairwise comparisons of MEDI17352 CCI and CCI doses versus placebo
 
 
 
• Supportive analysis 
 
○ Pairwise comparisons of MEDI17352 CCI and CCI doses versus placebo
 
 
 

Key secondary endpoints:  Change in the WOMAC pain subscale from baseline to week 12
	
MCP-MOD for:
 
 
• Other analysis 
 
○ Presence of dose response effect for each of the 6 prespecified candidate dose model.
 
 
 
• Supportive analysis 
 
○ Estimation of the dose-response parameters and target dose of MEDI17352 from the chosen model
 
 
 
 
ANCOVA for:
 
 
• Other secondary analysis 
 
○ Pairwise comparisons of MEDI17352 CCI and CCI doses versus placebo
 
 
 
• Supportive analysis 
 
○ Pairwise comparisons of MEDI17352 CCI and CCI doses versus placebo
 
 
 

Change in the WOMAC physical function subscale from baseline to week 12

ANCOVA for:

- **Other secondary analysis**
  - Pairwise comparisons of MEDI17352 CCI and CCI doses versus placebo
- **Supportive analysis**
  - Pairwise comparisons of MEDI17352 CCI and CCI doses versus placebo

Change in the PGA of OA from baseline to week 12

ANCOVA for:

- **Other secondary analysis**
  - Pairwise comparisons of MEDI17352 CCI and CCI doses versus placebo
- **Supportive analysis**
  - Pairwise comparisons of MEDI17352 CCI and CCI doses versus placebo

---

ANCOVA, Analysis of covariance; MCP-Mod, Multiple comparison procedure modelling; NRS, numerical rating scale; OA, osteoarthritis; PGA, Patient’s Global Assessment; WOMAC, Western Ontario and McMaster Universities Osteoarthritis.

#### 4.2.1.1 Multiple testing strategy

To control the overall family-wise type 1 error at 2.5% (1-sided) across primary and key secondary endpoints for pairwise testing, the sequentially rejective multiple comparison approach will be used as described by Bretz et al (2009).

Once the statistical significance is demonstrated for MCP-Mod statistical testing hypothesis for the primary endpoint as defined in section 4 then the testing process will commence for the remaining pre-defined hypotheses as summarised in Table 9 below.

**Table 9 Pre-defined hypothesis and hierarchy to be tested**

Hypothesis #	Endpoint	Test of:
H1	Change from baseline in weekly average NRS scores to week 12	Dose-response effect
H2	Change from baseline in weekly average NRS scores to week 12	Pairwise comparison: Difference between MEDI17352 CCI vs placebo
H3	Change from baseline in weekly average NRS scores to week 12	Pairwise comparison: Difference between MEDI17352 CCI vs placebo
H4	Change from baseline in WOMAC pain subscale scores to week 12	Dose-response effect
H5	Change from baseline in WOMAC pain subscale scores to week 12	Pairwise comparison: Difference between MEDI17352 CCI vs placebo
H6	Change from baseline in WOMAC pain subscale scores to week 12	Pairwise comparison: Difference between MEDI17352 CCI vs placebo
H7	Change from baseline in WOMAC physical function subscale scores to week 12	Pairwise comparison: Difference between MEDI17352 CCI vs placebo

H8	Change from baseline in WOMAC physical function subscale scores to week 12	Pairwise comparison: Difference between MEDI7352 CCI vs placebo
H9	Change from baseline in PGA of OA to week 12	Pairwise comparison: Difference between MEDI7352 CCI vs placebo
H10	Change from baseline in PGA of OA to week 12	Pairwise comparison: Difference between MEDI7352 CCI vs placebo

Hypotheses 2 to 10 will be tested using the sequential graphical weighted-Bonferroni approach described in Figure 2. The sequence isn't fixed as such but adapts to the result of testing of each hypothesis as specified in Figure 2 which also details the sequence of the formal statistical testing with the respective weights Bretz et al (2009).

The nominal p-values for all statistical hypotheses testing as per the section 4 will be presented in the outputs. However, if the null hypotheses are not rejected by the formal testing approach described above then no inference will be drawn from the nominal p-values.

**Figure 2 Formal statistical testing strategy**

[figure not shown]

Figure 2 shows that full 1-sided alpha ( $p=0.025$ ) is spent on the primary analysis (NRS Dose-Response test). Alpha is shared between doses for pairwise testing but weighted by power i.e., more allocated to CCI compared to CCI. If NRS Dose-Response is significant, then test NRS Pain pairwise and WOMAC Dose-response simultaneously i.e. not all alpha is used for pairwise testing of NRS.

Generally, for any given endpoint, alpha is allowed to pass between low and high doses for pairwise testing.

Specifically, WOMAC pain is only tested if the WOMAC pain Dose-Response test is statistically significant. And WOMAC function is only tested if WOMAC pain is statistically significant on the same dose. Finally, if WOMAC function is statistically significant on a given dose then alpha is passed to WOMAC endpoints on other dose and PGA of OA on same dose, but with lower weight for the test of PGA of OA.

#### **4.2.1.2 Analysis of the primary and key secondary endpoints**

##### **4.2.1.2.1 Primary endpoint**

The primary endpoint is the change in weekly average of daily NRS pain scores from baseline to Week 12.

A summary table of the weekly average of daily NRS pain score will provide summary statistics on baseline and the change from baseline to Week 12 for:

- ‘Observed cases’ only (i.e. no imputation methods applied)
- According to single imputations (combination of LOCF/BOCF only)
- ‘Observed cases’ only (i.e. no imputation methods applied) by ADA positive and negative participants as defined in section 3.4.2.

In addition, a figure presenting change from baseline in NRS weekly average pain scores over time per treatment arm, based upon observed data and the mean of the multiply imputed datasets, will be produced as well as a figure of the cumulative distribution function of change from baseline for observed cases, with horizontal axis truncated to only show improvement. Finally, the NRS weekly averages will be listed.

##### **4.2.1.2.1.1 Primary analysis of the primary endpoint**

The primary efficacy analysis aims at evaluating the dose response relationship of the change in weekly average of daily NRS pain scores from baseline to Week 12. The main statistical analysis will use the MCP-Mod methodology to test the statistical hypothesis presented in section 4.

## Multiple comparison procedure modelling (MCP-Mod)

There are two main steps to MCP-Mod:

- The ‘MCP’ step is a rigorous method used to establish the presence of a dose response while protecting the type I error and, if the dose-response relationship is statistically significant, then
- The ‘Mod’ step uses the selected candidate model(s) to produce inference on adequate doses, employing a model-based approach. That is producing estimates of the dose response function and associated model parameters, such as  $ED_{50}$  in the case of  $E_{max}$  relationship.

The underlying model will be an ANCOVA with dependent variable ‘change from baseline to Week 12’, and independent variables will include dose, ‘baseline score’ and KL grade at baseline as reported by Bioclinica. The random error is assumed to be normally and independently distributed with constant variance.

The KL grade covariate records the severity of knee OA using five grades (0-4) which are expected to be  $\geq 3$  at baseline, where 3 corresponds with moderate (moderate multiple osteophytes, definite narrowing of joint space and some sclerosis and possible deformity of bone ends) and 4 corresponds with severe (large osteophytes, marked narrowing of joint space, severe sclerosis, and definite deformity of bone ends).

According to Bornkamp B., Bezlyak V., and Bretz F.; 2015, these MCP and Mod steps can be further broken down as detailed below.

### Step 1: Set of candidate dose-response shapes

This step has been established at the trial design stage, where 6 candidates from three dose-response model types were selected as follows:

Model Name	Model $f(d, \theta)$	$\theta_2$ (shape of the model)
$E_{max}$	$E_0 + E_{max}d / (d + ED_{50})$	$ED_{50} (CCI)$ $ED_{50} (CCI)$ $ED_{50} (CCI)$
Linear	$E_0 + \delta d$	

Exponential	$E_0 + E_1(\exp(d/\delta) - 1)$	$\delta$ (CCI), corresponding to 10% of the maximum drug effect at CCI $\delta$ (CCI), corresponding to 25% of the maximum drug effect at CCI
-------------	---------------------------------	--

Where:

- $\mu(d, \theta) = \theta_0 + \theta_1 f^0(d, \theta_2)$  with  $q_0$  and  $q_1$  parameters that determine the location and scaling of the function  $f$ , and  $f^0(d, q_2)$  is a nonlinear transformation of the dose levels depending on  $q_2$
- $E_0$  is the basal effect at  $d=0$
- $E_1$  is the scale parameter in the exponential model
- $d$  is the dose
- $ED_{50}$  is the dose that gives 50 percent of the maximum effect
- $d$  is the rate of change for linear and exponential models

### Step 2: Calculation of optimal contrasts and dose response parameters

Optimum contrast coefficients will be computed for each model to maximize the marginal power to detect a specific dose-response shape that is associated with the corresponding candidate model (Bornkamp B., Bezlyak V., and Bretz F.; 2015).

The computation of optimal covariate-adjusted contrasts is achieved by %optcont macro using the combined estimated covariance matrix  $\hat{S}$  (Pinheiro et al.; (2004) and the candidate models. This matrix and estimated dose response parameters ( $\hat{\mu}$ ) are generated using the estimated LSMEANS ( $\hat{\mu}^{(q)}$ ) and covariance matrices of the LSMEANS  $\hat{S}^{(q)}$  extracted from PROC GENMOD performed on multiply imputed datasets and then combined using the Rubin’s rule (Shomaker and Heumann, 2014) as described in section 4.1.1.1. SAS example code to execute this step (excluding imputation) can be found in [Appendix D1](#) .

### Step 3: Dose response signal detection

The significance of the individual candidate dose-response model is tested in this step. This is done in terms of multiple linear contrast tests based on the optimal contrast coefficients calculated above. The significance of the individual candidate dose-response shapes will be evaluated based on the statistical hypotheses presented in section 4 where the individual test statistic and corresponding p-value for each candidate model are calculated using the estimated covariance matrix  $\hat{S}$ , the contrasts coefficients and the estimated dose response parameters calculated in step 1 using the methodology detailed in [Appendix D2](#).

Consequently, if the minimum adjusted p-value for the optimal contrasts for the candidate models is less than alpha (0.025), the null hypothesis will be rejected and the proof of concept of a non-null dose-response will be demonstrated.

PROC IML will be used to calculate the test statistics and corresponding p-values since it allows for the multiplication of vectors and matrices and sampling from a multivariate normal distribution. The seed 568000003 will be used when sampling from the multivariate normal distribution. Example SAS code is also included in [Appendix D2](#).

If none of the candidate models are statistically significant, the procedure stops, suggesting that a dose-response relationship cannot be established from the observed data. However, in such circumstances the dose-response model corresponding to the MCP test contrast with the lowest p-value will still be estimated.

#### **Step 4: Model selection**

Out of the statistically significant candidate models the most appropriate one will be selected using the model selection criteria gAIC. Additional information alongside an example code can be found in [Appendix D3](#).

The best/optimal model will be the one with the minimum gAIC criterion. The gAIC for each model will be displayed in the table and the optimal model with the minimum gAIC will be indicated.

#### **Step 5: Dose-response and dose estimation (Target dose selection)**

The estimates from the optimal dose-response model will be used to calculate the minimum effective dose (MED), ED50, 90% of the Emax (ED90) and dose to achieve selected target effects if/when applicable. The MED is defined as the minimum dose that the chosen model predicts will achieve 1.0, 1.2 and 1.5-point improvements over placebo. For details concerning the derivations of MED and other parameters refer to the [Appendix D4.1](#).

To obtain the 95% CIs for the MED and estimates other than model estimates of the treatment effect at doses studied, the asymptotic normal distribution of the estimates from the optimal dose-response model will be determined as per [Appendix D4.2.1](#). 10,000 samples from the asymptotic normal distribution will then be drawn (using seed 568000003) with each set of samples used to create a dose response curve and corresponding MED. The 0.025 and 0.975 percentiles of the MED values will be used to form the 95% confidence intervals. Same approach will be used to obtain the 95% CIs for estimates other than model estimates of the treatment effect at doses studied.

The 95% CIs for estimates associated with treatment comparisons will be constructed using the delta method described in [Appendix D4.2.2](#).

Finally, the MCP-Mod process will be reported in a summary table including:

- Candidate dose-response models test statistics (including adjusted p-value)
- gAIC values for all candidate dose-response models (lowest value shows model with best fit)

- Model parameter estimates such as Emax, ED50, slope, delta, E1 with their corresponding 95% CIs
- Minimum effective doses: MED 1.0, 1.2 and 1.5 and ED90 with their corresponding percentile-based 95% CIs only for optimal model with the lowest gAIC. There will be two types of ED90 estimated. The first applies to all models and is defined as the dose needed to produce 90% of the effect of the highest dose and the “asymptotic ED90”, which is only applicable to the Emax model. Therefore the “asymptotic ED90” and corresponding CI will be computed only if Emax model is selected as optimal model.
- Model estimates of the treatment effect at doses studied together with 80% and 90% 1-sided confidence intervals as well as 95% CIs only for optimal model with the lowest gAIC.

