## Appendix D4 Model estimates

### Appendix D4.1 Calculation of Dose to achieve target effects

Target Dose  $TD_{\Delta}$  to achieve a Delta ( $\Delta$ ) versus placebo (MED):

Linear:  $TD_{\Delta} = \Delta / \delta$ , where  $\delta$  = estimated linear slope

Emax:  $TD_{\Delta} = ED_{50} / ((E_{max} / \Delta) - 1)$ , where  $ED_{50}$  and  $E_{max}$  are estimated from the fitted Emax model

Exponential:  $TD_{\Delta} = \delta * \log((\Delta / E_1) + 1)$ , where  $\delta$  and  $E_1$  are estimated from the fitted exp model

Dose ( $ED_P$ ) to achieve a certain proportion P of the effect of the maximum dose studied versus placebo

Linear:  $ED_P = P * \max(\text{Doses}) = P * 150$

Emax:  $ED_P = (P * ED_{50} * \max(\text{doses})) / (ED_{50} + (1 - P) * \max(\text{doses})) = (P * ED_{50} * 150) / (ED_{50} + (1 - P) * 150)$

Exponential:  $ED_P = \delta * \log((P * \exp(\max(\text{doses}) / \delta) - P + 1)) = \delta * \log((P * \exp(150 / \delta) - P + 1))$

Note: Protocol defines  $ED_P$  as the proportion P of the asymptotic maximum effect ( $E_{max}$ ) for the Emax model that will be determined as follows:

Emax: asymptotic  $ED_P = (P * ED_{50}) / (1 - P)$

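### The MED is obtained by inverting the fitted curve with no limit at the highest studied dose and no rule for an unreachable target, so it can come out above 150 or negative, and its percentile interval inherits this

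*SAP*

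**What the plan says.** Step 5 of section 4.2.1.2.1.1 gives the definition: "The MED is defined as the minimum dose that the chosen model predicts will achieve 1.0, 1.2 and 1.5-point improvements over placebo". It also promises the "dose to achieve selected target effects if/when applicable" and refers to Appendix D4.1 for the derivations. The MCP-Mod summary table is to show the three MEDs, with percentile-based 95% intervals, for the model with the lowest gAIC.

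Appendix D4.1 calls the quantity a target dose and gives one closed formula per model. The linear formula is "TD_{\Delta} = \Delta / \delta", where δ is the "estimated linear slope". The Emax and exponential formulas are the corresponding inversions. None carries an upper bound or a condition on its use. The same appendix does use the highest dose, 150 (units not shown), in its formulas for the dose giving a proportion P of the top-dose effect.

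For the interval, Step 5 draws 10,000 parameter sets from the asymptotic normal distribution, computes an MED from each, and takes the 0.025 and 0.975 percentiles.

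Two ED90s are planned. One is relative to the effect of the highest dose. The other is asymptotic and "will be computed only if Emax model is selected as optimal model".

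**The concern.** All three model types are monotone. If the fitted effect at 150 is below the target, no studied dose reaches it, and the informative result is that the target was not reached in the studied range. The formulas print a number anyway. It is either a dose beyond anything given in the trial, resting only on the assumed curve, or a negative dose, which has no meaning.

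This can happen with ordinary results. Section 5 works with a target value of 1.5 points and a lower reference value of 0.8. Every fitted top-dose effect between those values makes the MED for 1.5 points invalid or an extrapolation. Step 3 also has a model estimated when no contrast is significant, and small fitted effects are then likely.

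The interval has a further problem. A negative draw that means the target is unreachable belongs at the high end of the ordering, but raw percentiles put it at the low end.

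**Working it through.** The SAP states no MED value, so there is no figure to reproduce.

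**Inputs.** The highest dose, 150, is written into the D4.1 formulas. The targets 1.0, 1.2 and 1.5 come from Step 5. The ED50 values 10, 40 and 80 come from the example code in Appendix D1 and serve only as example shapes. The effect *e* at 150 is assumed. Improvements are written as positive numbers.

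**Formulas (D4.1), target Δ.**
- Linear: Δ / slope, with slope = *e*/150.
- Emax: ED50 / (Emax/Δ − 1), with Emax = *e* × (150 + ED50)/150.
- Exponential: δ × log(Δ/E1 + 1), with E1 = *e*/(exp(150/δ) − 1).

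**MED for 1.5 points, with *e* = 1.2.**
- Linear: 1.5/(1.2/150) = 1.5/0.008 = 187.5.
- Exponential, δ = 25: 155.6.
- Emax, ED50 40: Emax = 1.2 × 190/150 = 1.52; 40/(1.52/1.5 − 1) = 40/0.01333 = 3000.
- Emax, ED50 10: Emax = 1.2 × 160/150 = 1.28, below 1.5; 10/(1.28/1.5 − 1) = 10/(−0.1467) = about −68.

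**MED for 1.0 / 1.2 / 1.5 points at other effects.**

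| Effect at 150 | Linear | Emax, ED50 10 | Emax, ED50 40 | Emax, ED50 80 |
|---|---|---|---|---|
| 0.8 | 187.5 / 225 / 281 | −68 / −35 / −23 | 3000 / −257 / −123 | 353 / 3600 / −439 |
| 1.0 | 150 / 180 / 225 | 150 / −90 / −35 | 150 / 720 / −257 | 150 / 288 / 3600 |
| 1.5 | 100 / 120 / 150 | 17 / 30 / 150 | 44 / 69 / 150 | 62 / 87 / 150 |

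The MED lies within 0 to 150 exactly when the fitted effect at 150 is at least the target. Otherwise the linear and exponential formulas exceed 150. The Emax formula exceeds 150 if Emax is above the target and is negative if Emax is below it.

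**Interval (illustration only).** The assumptions are 51 per arm (255/5, from section 1.3), residual SD 2.0, true effect 1.2 at 150 and ED50 40. Drawing from the Appendix D4.2.1 distribution, about 21% of draws for MED 1.2 were negative and about 30% exceeded 150. Two separate runs gave 95% limits of about −807 to 1103 and −936 to 989. Over SD 2.0 to 2.5, effects 1.0 to 1.5 and the three ED50s, 11% to 69% of MED draws were negative and 2% to 59% exceeded 150.

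Not every negative draw means that the target is unreachable. The normal distribution also allows a negative ED50, which is not an admissible curve. In the scenario above the asymptotic ED90 limits were −608 and 1316; dividing by 9 gives ED50 limits of about −68 and 146.

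**The case against.** The strongest points on the other side:

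- **Supportive status.** Table 8 classes target-dose estimation as supportive. No hypothesis, alpha allocation or stated decision rule uses the MED; the interim rules in section 5 use model-based differences from placebo. This stands and limits the weight of the point.
- **Visibility.** The same table shows model-estimated effects at the studied doses, so a careful reader can see a top-dose effect below the target. That is true, but it does not make a negative dose or a mis-ordered interval usable.
- **The applicability phrase.** It could be read as covering unreachable targets. It gives no criterion, and may only mean that some quantities belong to some models.
- **Unseen material.** The output shells are not shown and some appendix code is redacted, so a display convention there cannot be excluded. However, Step 5 sends the reader to D4.1, which is readable and has none.

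A reader might also infer that the asymptotic ED90 is defective, since it equals 0.9 × ED50/0.1 = 9 × ED50, or 360 and 720 for ED50 40 and 80. The documents do not support that. It is labelled asymptotic, follows the protocol's definition as D4.1 reports it, and sits beside an ED90 that cannot exceed 150. D4.1 does not call it a target dose. The 360 and 720 also rest on example-code shapes, not fitted values.

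**Conclusion.** The gap is real for the MED and its interval. It follows from the stated formulas by arithmetic and needs no assumption about variability. Whenever the fitted effect at 150 is below the target, the plan yields an extrapolated dose (187.5 or 3000 in the examples) or an impossible one (about −68), and the percentile limits can be distorted in the same way.

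How often this would occur cannot be taken from the SAP, which gives no residual SD and no true effect or curve shape. The simulated shares and limits are illustrations under the stated assumptions. A reader might infer that an out-of-range MED is the expected result or that the primary conclusion is at risk. Neither follows: with a fitted effect of 1.5 or more at 150 all three point estimates are within range, and the MCP test does not use the MED. The size is that of a reporting rule worth fixing for a supportive analysis.

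**What to change.** In Step 5 and Appendix D4.1:

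1. Define the MED as the smallest dose in 0 to 150 at which the selected model reaches the target. If it does not, report 'not reached in the studied dose range (>150)'.
2. For the interval, treat every draw whose curve does not reach the target by 150, including draws giving a negative or undefined MED, as >150 and rank it highest. Report a limit falling there as '>150'. State how draws with a non-positive ED50 are handled if sampling is not bounded.
3. At most, footnote the asymptotic ED90 as extrapolated when it exceeds 150. No change to its definition is needed.

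In the illustration, about 21% + 30% = 51% of draws would count as >150. The upper limit would then read '>150', and the lower limit would fall among the remaining draws, inside 0 to 150.

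The cost is a few sentences and one condition in the program. The downside is that some cells show '>150' or 'not reached' instead of a number.

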**Appendix D4.2.1 Asymptomatic normal Distribution**

Sampling from the asymptotic normal distribution is used for constructing all 95% CIs except those for model estimates of the treatment effect at doses studied.

The parameters from the selected model are asymptotically normally distributed, following the distributed given below as described in Pinheiro et al (2014).

$$MNV \left( \hat{\theta}, \left[ F(\hat{\theta})S^{-1}F(\hat{\theta})^T \right]^{-1} \right)$$

Where  $F(\theta_0)$  is a  $d \times k$  matrix of the partial derivatives  $\frac{\partial f(x_i, \theta)}{\partial \theta_h}$   $i = 1, \dots, k$   $h = 1, \dots, d$  with each row being the partial derivative at each parameter and each column being the value of that derivative for a given dose.

As an example,  $F(\theta_0)$  for the linear dose response candidate model with no additional covariates is given below where  $\theta = \begin{pmatrix} E_0 \\ \delta \end{pmatrix}$ ; CCI 

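### With an Emax fit, the percentile interval for the minimum effective dose mixes in invalid draws: lower limits go negative, and a finite upper limit can be printed where none exists

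*SAP*

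**What the plan says.** Step 5 of SAP Section 4.2.1.2.1.1 sets three targets: "The MED is defined as the minimum dose that the chosen model predicts will achieve 1.0, 1.2 and 1.5-point improvements over placebo". For the interval it takes 10,000 draws, "with each set of samples used to create a dose response curve and corresponding MED", and then: "The 0.025 and 0.975 percentiles of the MED values will be used to form the 95% confidence intervals". The same approach is used for the other estimates apart from treatment effects at the studied doses, so it also covers ED50 and ED90.

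Appendix D4.2.1 gives the sampling distribution: "The parameters from the selected model are asymptotically normally distributed", centred at the estimates, with covariance [F S⁻¹ Fᵀ]⁻¹. ED50 is on its natural scale, with no log and no bound.

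Appendix D4.1 gives the MED formulas without conditions:

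- Linear: Delta/δ
- Emax: ED50/((Emax/Delta) - 1)
- Exponential: δ·log((Delta/E1) + 1)

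The only qualifier in Step 5 is that estimates are produced if or when applicable. That concerns which quantities are calculated, not what to do with an invalid draw.

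**The concern.** Each formula gives a dose only for a curve that reaches the target. A normal draw on the natural scale need not be such a curve. In the Emax model two things can go wrong:

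- **ED50 is drawn below zero.** If Emax exceeds the target in size, the formula returns a negative dose.
- **Emax is drawn short of the target.** The target is never reached and the MED is infinite, yet the formula returns a finite number. It is negative if ED50 is positive, and positive and plausible-looking if ED50 is negative.

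Raw percentiles take all of these at face value. A negative lower limit is visibly wrong. A finite upper limit that ought to be open is harder to spot and hides the fact that the data do not bound the dose. Step 5 concerns target dose selection, the MEDs at 1.0, 1.2 and 1.5 points are named table outputs, and three of the six candidate shapes are Emax. Step 3 also has a model estimated when no candidate is significant, which is where invalid draws are most common.

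**Working it through.** **The formula on single draws** (Delta = -1, benefit negative):

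- Emax -0.8, ED50 40: 40/(0.8 - 1) = -200. The target is unattainable.
- Emax -1.9, ED50 -10: -10/(1.9 - 1) = -11.1. Emax is large enough, but ED50 is invalid.
- Emax -0.8, ED50 -10: -10/(0.8 - 1) = +50. Invalid on both counts, yet it looks like a usable dose.

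The algebra is correct for a valid curve: with Emax -1.9 and ED50 40 the formula returns 44.4, where the effect is exactly -1.0.

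**Inputs from the SAP.** Doses 0, 7.5, 25, 75, 150 and a candidate ED50 of 40 (code in Appendix D1). Sample size from Sections 1.2 and 1.3: 255/5 = 51 per arm at the information target, 350/5 = 70 per arm at the maximum.

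**Assumptions, because the SAP gives no figure.** SD 2.0 or 2.5; fitted Emax -2.0 (effect -2.0 × 150/190 = -1.58 at the top dose), with -3.0 as a larger effect; S = (SD²/n)·I. The SAP states no MED or interval to reproduce.

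**Standard errors.** With 51 per arm and SD 2.0, [F S⁻¹ Fᵀ]⁻¹ gives SE(Emax) = 0.598 and SE(ED50) = 41.3. Both scale with SD/√n. From the normal distribution:

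- P(ED50 < 0) = Φ(-40/41.3), about 17%
- P(Emax short of 1.0) = Φ(-1.0/0.598), about 4.7%
- P(Emax short of 1.5) = Φ(-0.5/0.598), about 20%

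**Step 5 applied literally (Emax -2.0, ED50 40, point MED 1.0 = 40):**

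| n per arm, SD | MED 1.0 interval | Never reach 1.0 | Never reach 1.5 |
|---|---|---|---|
| 70, 2.0 | about (-84, 136) | 2.5% | 16% |
| 51, 2.0 | about (-136, 192) | 4.7% | 20% |
| 51, 2.5 | about (-230, 300) | 9% | 25% |

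Limits move by a few units between runs for MED 1.0, and by more for MED 1.5, whose interval is about (-640, 820) at 51 per arm and SD 2.0, around a point estimate of 120.

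**Where the negative values come from** (51 per arm, SD 2.0). For MED 1.0, 14.3% of draws are negative. Of these, 13.0 points have ED50 < 0 with Emax large enough, and only 1.2 points have Emax short with ED50 > 0. Of the roughly 4.8% of draws that fall short, 3.6 points have ED50 < 0 and so return a positive dose. For MED 1.5, about 20% fall short and about half of them return a positive dose.

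**Larger effect.** With Emax -3.0 (51 per arm, SD 2.0), SE(ED50) = 41.3 × 2/3 = 27.5 and Φ(-40/27.5) is about 7%. Only 0.04% of draws fall short of 1.0. The MED 1.0 interval is about (-12, 39.7), and the upper limit is the same whether or not short draws are counted as infinite.

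**Wider check.** A grid of 36 Emax settings (51 or 70 per arm; SD 2.0 or 2.5; ED50 10, 40, 80; effect at 150 of -1.0, -1.5, -2.0) gave a negative lower and a finite upper limit every time. The mildest MED 1.0 interval was (-1, 23). In simulated trials with a significant MCP test, the MED 1.0 lower limit was negative in 99-100%. More than 2.5% of draws were non-attaining in 47-100% of those trials, across settings. These simulations used a known SD, no covariates or imputation, and always fitted Emax.

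**Other models.** Exponential: if Delta/E1 < -1 the log has a negative argument, e.g. E1 = 0.5, Delta = -1 gives log(-1). Linear: only a wrong-signed slope matters. With 51 per arm, SD 2.0 and -1.5 at 150, z = 4.45 and the MED 1.0 interval is (70, 178). With SD 2.5 and -0.8, z = 1.90 and it becomes (-438, 1225).

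**ED50 and ED90** (51 per arm, SD 2.0, Emax -2.0). ED50: 40 ± 1.96 × 41.3 = (-41, 121). Asymptotic ED90 is 9 × ED50, so about (-370, 1090).

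**The case against.** Four objections carry weight.

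1. **Scope.** The output is supportive in Table 8, and the MCP test, the pairwise tests and the model-based effects at studied doses do not use these percentiles. This stands. A reader might infer that the trial's primary inference is damaged; nothing in the SAP supports that.

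2. **Direction of the error.** A reader might infer that non-attaining draws all sort in as very low doses, so that the upper limit is always too small. The calculation does not bear this out. Half to three quarters of those draws return a positive dose in the worked case, most negative values for MED 1.0 come from ED50 < 0, and with Emax -3.0 the MED 1.0 upper limit does not move. Nor is every model affected: the linear interval is sound unless the slope is weak.

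3. **The definition may already exclude such draws.** A curve that never reaches the target has no MED under the Step 5 definition, and parts of the appendix code are redacted. But the visible rule forms an MED from each draw and takes percentiles of those values. Step 5, D4.1 and D4.2.1, where a rule for invalid draws would belong, contain none. Handling in redacted code cannot be excluded.

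4. **A reader would notice.** A negative dose limit, or an upper limit above the top dose of 150, signals failure. That is partly true, but 136 in the table lies within the studied range, and a finite limit does not tell the reader that the true limit is open.

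**Conclusion.** The point holds for the Emax model, and in a limited way for the other two. Step 5 followed as written gives a negative MED lower limit in every Emax setting tried, mainly through ED50 < 0 for the 1.0-point target. It reports a finite upper limit even when more than 2.5% of draws never reach the target. For Emax -2.0 and ED50 40 the non-attaining share is about 2.5% to 9% at 1.0 point, so the first row of the table sits at the threshold, and 16% to 25% at 1.5 points, where no finite upper limit exists. With Emax -3.0 only the lower limit of MED 1.0 is clearly invalid. The exponential MED can be undefined, and the linear MED fails only with a weak slope. SD and effect size are assumptions; the finding of invalid lower limits did not depend on them over the range shown. This is worth correcting because MED is the dose-finding output, but it concerns estimation, not type I error.

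**What to change.** In Step 5 and Appendices D4.1 and D4.2.1:

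- Estimate and sample ED50 (Emax) and delta (exponential) on the log scale, so that draws stay positive.
- Set the MED of a draw to +infinity when its curve does not reach the target improvement.
- Report a limit as 'not reached' when that percentile is infinite, and give the share of non-attaining draws for each target.
- State that Delta carries the sign of benefit on the modelled scale. Section 3.1.3 defines change as post-baseline minus baseline, which would make it negative. The Appendix D1 example call uses an increasing direction, so the visible text leaves the sign open.

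The first two steps are both needed: the infinity rule alone leaves negative lower limits from ED50 < 0, and log sampling alone leaves non-attaining draws with finite values. The log scale also repairs the ED50 and ED90 lower limits. The cost is a few lines of code and wording, and some upper limits will read 'not reached'.
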